### **A. Background:**

Enhanced recovery after surgery (ERAS) has become the standard of care for patients undergoing surgery for gynecological malignancies after the ERAS guidelines for gynecologic oncology were widely disseminated in 2016. Regional analgesia can be a part of a multimodal analgesic regimen leading to opioid-sparing effects. While epidurals are effective for pain control, they may slow postoperative mobility, delay return of bowel function, prolong the need for urinary catheters, result in transient hypotension, and may be ineffective in as many as 50% of patients. Alternate opioid sparing modalities include intrathecal analgesia and incisional local anesthetic infiltration.

Intrathecal analgesia (ITA) has been shown to shorten time to return of bowel function and length of hospital stay when compared to epidural analgesia. Intrathecal analgesia is known to be effective after cesarean delivery; preservative free morphine in a dose of 100 to 200 $\mu$ g is the most commonly used agent. Following a national shortage of preservative-free morphine, intrathecal hydromorphone has been explored as a potential alternative for postoperative analgesia. Hydromorphone is more lipophilic than morphine which may allow for a favorable side effect profile. Intrathecal analgesia is being incorporated into ERAS protocols to decrease postoperative opioid consumption.

In our practice, wound infiltration with liposomal bupivacaine is the cornerstone of treatment of early postoperative pain within our ERAS pathway, and resulted in a reduction in patient-controlled analgesia from 33.35 to 4.1% (P<.001) in patients undergoing laparotomy and complex cytoreduction for ovarian cancer. The advantages of wound infiltration are that it is quick, simple, inexpensive, and consistently effective. Intrathecal analgesia is currently used in less than 1% of our patients.

Given that visceral pain which can be significant in tumor debulking is not targeted by incisional bupivacaine, combining ITA with incisional liposomal bupivacaine (ILB) to provide more intensive pain relief in the first 24 hours is a viable option. However, it is unclear if patient experience with pain management is improved with ITA given that opioid related side effects (nausea, vomiting, itching) as well as rare adverse events related to spinal injections (postural puncture headache) can occur. Additionally, ITA is invasive and expensive. The purpose of this investigation is to evaluate whether ILB is non-inferior to a combination of ITA and ILB for management of postoperative pain after laparotomy for gynecological malignancy within an established enhanced recovery pathway using the Overall Benefit of Analgesia Score (OBAS) as our primary outcome. Additionally, we will evaluate cumulative 24 hour postoperative morphine milligram equivalents (MME) consumption, pain scores, length of stay, cost, and patient satisfaction as secondary outcomes.

### **B. Hypothesis and Aims**

**Hypothesis:** Among women undergoing laparotomy for gynecological malignancy, the pain experience (as measured by the OBAS) of those randomized to no additional intervention will be non-inferior to

that of patients randomized to ITA with 150mcg of hydromorphone within an established enhanced recovery pathway which includes incisional ILB (in both arms).

### **Specific Aims**

1. Evaluate if no additional intervention is noninferior to ITA for postoperative pain experience 24 hours after surgery after laparotomy for gynecological malignancy within an established enhanced recovery pathway which includes ILB.
2. Evaluate the effect of intrathecal analgesia on patient satisfaction with postoperative analgesia after laparotomy for gynecological malignancy.
3. Report the impact of ITA use on cost.
4. Validate the QOR-15 in our population

### **C. Research plan and methods:**

#### **C.1 Study design:** Randomized controlled study

##### Randomization:

1. Stratified by:
  - a. Likelihood of bowel resection  $\geq 50\%$  or  $<50\%$  as assessed by surgeon
  - b. Planning to use NSAIDs vs not planning to use NSAIDs
2. Allocation ratio- 1:1
3. Allocation sequence- permuted block randomization with varying block sizes ( Provided by statistician in the Department of Biostatistics and Informatics)

Blinding: None

Allocation concealment method: web-based

#### **C.2 Population, intervention, comparator, and outcomes**

##### **Population:**

Women undergoing laparotomy for gynecological malignancy

Inclusion: age  $>18$ yo and  $\leq 80$ yo, elective surgery for suspected (based on consulting surgeon's opinion-imaging, lab, path) gynecological malignancy, ERAS protocol

##### Exclusion:

1. Inability to read or understand English
2. Prehospitalization narcotic use if weekly average daily oral morphine equivalent of  $>20$  mg.
3. Chronic pain syndromes such as fibromyalgia.
4. Extensive surgery planned (surrogate for postop pain): Planned ICU admission, abdominoperineal resection, exenteration, use of IORT, HIPEC
5. Contraindication to neuraxial analgesia:
  - a. Coagulopathy
    - i. INR  $>1.2$  Current or predicted after surgery (e.g. planned right hepatic resection)
    - ii. Thrombocytopenia. plts  $<100$ .
    - iii. Hemophilic disease states (hemophilia, von Willebrand disease, etc.)

- iv. Patients receiving antithrombotic or thrombolytic therapy are excluded according to the ASRA guidelines (Reference:  
<https://rapm.bmjjournals.org/content/rapm/43/3/263.full.pdf>)
- b. Localized infection at the potential site of injection
- c. Significant developmental or structural spinal abnormalities that would preclude a safe spinal technique. These include spina bifida, tethered spinal cord, lumbar spinal fusion, and active lumbar radiculopathy.
- 6. Patients with stage 4 or 5 kidney disease (GFR less than 30 ml/min per 1.73 m^2).
- 7. Intolerance or allergy to opioids, acetaminophen, or amide-type local anesthetics
- 8. Current pregnancy

**Intervention:** ITA with 150mcg of hydromorphone in addition to ILB. For patients randomized to ITA, injection will be performed in the O.R.

**Comparator:** ILB

Standardized perioperative anesthetic protocol (Appendix A) and postoperative protocol (Appendix B) will be used

**Outcomes:**

Primary outcome:

Overall Benefit of Analgesia Score (OBAS): The OBAS will be administered in the form of a questionnaire to be filled out by the participants at baseline (preoperatively) and at 24 hours ( $\pm 2$  hours) postoperatively. The OBAS consists of 7 items that assess pain intensity, opioid-related adverse effects and patient satisfaction with pain management. The composite score ranges from 0 (best) to 28 (worst).

Secondary outcome:

Cumulative 24 hour narcotic consumption, measured in morphine metabolic equivalents (MME)

Postoperative pain scores (rest, movement) at 4, 8, 16 and 24 hours after surgery.

Time to first analgesic request

Use of intravenous patient-controlled analgesia

Use of IV rescue opioids

Length of stay

Fluid balance: Additional fluid requirement after 24 hours of surgery, weight gain following surgery

Cost of care

Adverse events:

Related to spinal injection: Puncture site bleeding/hematoma/infection; Spinal headache

Related to systemic opioid effects: Itching; Nausea/vomiting; Sedation; respiratory depression

Related to delayed recovery: Time to regular diet/Bowel movement, postoperative ileus, time to first ambulation, time to Foley removal, voiding dysfunction/ need for re-catheterization, readiness for discharge

Cost analysis:

OR time and surgical time

Total and pain management related standardized costs

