## **Appendix A: Standardized perioperative anesthetic protocol**

### Preoperatively:

1. Tylenol 1000 mg po, Celebrex 200 mg po.
2. No gabapentin administration unless patient is chronically preoperatively receiving medication. In such a scenario, the patient would take their normal gabapentin dose the morning of surgery
3. Scopolamine patches for patients at high risk for postoperative nausea and vomiting, oral caffeine for headache prophylaxis in caffeine users, and midazolam for anxiolysis can be administered at the anesthesiologist's discretion.
4. For those patients who will receive an intrathecal opioid (150 mcg of hydromorphone), midazolam and fentanyl may be administered for procedural sedation.

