### Intraoperatively:

1. The anesthetic will include induction with propofol and either succinylcholine or a non-depolarizing muscle relaxant. Maintenance will include volatile anesthetic/air/oxygen. A background propofol infusion may be administered for postoperative nausea and vomiting prophylaxis at the anesthesiologist's discretion.
2. No dexmedetomidine, lidocaine, ketamine or remifentanil infusions.
3. Intravenous fentanyl will be administered by the anesthesia team per the discretion of the anesthesiologist with a goal of no more than 500mcg fentanyl throughout the case.
4. Postoperative nausea prophylaxis with 8 mg of IV dexamethasone, 4 mg of ondansetron, 0.625 mg of droperidol, Ketamine 10 mg IV at the beginning and at the end of the case.
5. Ketorolac 15 mg IV may be given if stratified to "plan for NSAID use" at the anesthesiologist's discretion.

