#### **Appendix B. Postoperative pain Management**

1. Tylenol 1000mg po every 6 hours
2. Ketorolac 15 mg IV every 6 hours X 4 doses if stratified to "plan for NSAID use"
3. Ibuprofen every 6 hours if stratified to "plan for NSAID use", start 6 hours after the last Ketorolac dose. See table below for dose.

Ibuprofen dose	Weight <50 kg	Weight 50-80 kg	Weight >80 kg
Age <65	200	600	800 q 8 hours
Age >65	200	400	600

4. Oxycodone 5mg every 4 hours PRN for moderate pain or pain score of 4-6/10. Administer if pain is unrelieved by Tylenol. For patients who received intrathecal analgesia, start 24 hours after intrathecal dose was given.
5. Oxycodone 10mg every 4 hours PRN for severe pain or pain score of 7-10/10. Administer if pain is unrelieved by Tylenol. For patients that received intrathecal analgesia, start 24 hours after intrathecal dose was given.
6. Dilaudid 0.4mg IV every 2 hours PRN for breakthrough pain. To be given if pain is unrelieved 30 minutes after PRN oral medication is used; if unable to take oral pain meds; or if pain is greater than or equal to 7, use instead of oral pain medication.
7. Oral intake, timing of Foley catheter removal and ambulation in accordance to ERAS protocol and discretion of the surgeon.

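### In this unblinded trial the separately listed opioid adverse events have no definition and no common assessment times, so between-arm counts could reflect unequal ascertainment

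*Combined protocol and SAP*

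**What the plan says.** Section C.1 states "Blinding: None". In C.2, under Outcomes, the opioid-related harms appear as a bare list: "Related to systemic opioid effects: Itching; Nausea/vomiting; Sedation; respiratory depression". Neither that section nor any other gives a definition, grading scale, assessor, time point or window for them. A secondary outcome in the same section does have a schedule: "Postoperative pain scores (rest, movement) at 4, 8, 16 and 24 hours after surgery".

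One scheduled instrument touches on these effects. "The OBAS consists of 7 items that assess pain intensity, opioid-related adverse effects and patient satisfaction with pain management", and it is "to be filled out by the participants at baseline (preoperatively) and at 24 hours", with a window of 2 hours either side of the 24-hour point. The item text in Appendix C is not shown, so which effects it covers cannot be checked.

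Care in the first day differs by arm in two written ways. Appendix A (Preoperatively, item 4) allows midazolam and fentanyl for procedural sedation in patients receiving the intrathecal opioid. Appendix B, for oral oxycodone, says: "For patients who received intrathecal analgesia, start 24 hours after intrathecal dose was given".

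On antiemetics, Appendix A (Intraoperatively, item 4) sets a core prophylactic regimen without reference to arm. Around it sit two discretionary measures, "Scopolamine patches for patients at high risk for postoperative nausea and vomiting" and "A background propofol infusion may be administered for postoperative nausea and vomiting prophylaxis at the anesthesiologist's discretion", and rescue antiemetics in the PACU, also discretionary.

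The Statistical analysis plan compares categorical variables between arms by chi-square or Fisher's exact test.

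**The concern.** A count of adverse events compares treatments fairly only if both arms had the same opportunity to have an event seen and written down. Here staff know the allocation, the plan sets no common occasions for looking and no threshold for what counts, and early care is not identical in the two arms. A difference in recorded sedation or respiratory depression could then be a difference in charting, and a similarity could hide a real difference.

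The Background gives nausea, vomiting and itching as reasons why intrathecal analgesia (ITA) might not improve the patient's experience, so readers will look to these counts when weighing ITA plus incisional liposomal bupivacaine (ILB) against ILB alone. The analysis cannot repair the problem later. Without scheduled assessments an uncharted event is counted as no event, not as missing, so the planned multiple imputation does not reach it. The planned regression adjustment concerns baseline imbalance only.

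**Working it through.** The plan states no event rate or detection rate, so there is no figure of its own to reproduce on this point. The check is a comparison of provisions, then an illustration on assumed inputs.

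**1. What is fixed for each measure**
- Pain at rest and on movement: four set times, both arms.
- OBAS: baseline and 24 hours, both arms, completed by the participant, analysed as a mean composite score.
- Itching, nausea/vomiting, sedation, respiratory depression as adverse events: no times, no definition, no assessor. The plan does not say that they are to be taken from OBAS items.

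**2. Could opportunity for recording differ by arm?** Allocation is known. Appendix A (procedural sedation) and Appendix B (start of oral oxycodone) make first-day care depend on arm. This makes different attention plausible. It does not show that it will occur, or in which arm.

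**3. Possible size, on assumed inputs.** Let the true event rate p be the same in both arms, and let s be the share of true events recorded.
- Observed rate = p × s
- Spurious difference = p × (s₁ − s₂); spurious ratio = s₁ / s₂

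| p | s₁ | s₂ | Observed rates | Difference | Ratio |
|---|---|---|---|---|---|
| 0.10 | 0.90 | 0.80 | 0.09 v 0.08 | 1 point | 1.13 |
| 0.20 | 0.95 | 0.80 | 0.19 v 0.16 | 3 points | 1.19 |
| 0.20 | 0.95 | 0.70 | 0.19 v 0.14 | 5 points | 1.36 |
| 0.40 | 0.95 | 0.80 | 0.38 v 0.32 | 6 points | 1.19 |
| 0.40 | 0.95 | 0.70 | 0.38 v 0.28 | 10 points | 1.36 |

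If s₁ = s₂ the difference is zero. If the better-observed arm is the comparator, the sign reverses.

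**4. Set against sampling error.** The Sample size calculation plans 52 per arm (49 × 1.05 = 51.45, rounded up). The approximate 95% half-width for a difference is 1.96 × √[a(1−a)/52 + b(1−b)/52].
- 0.19 v 0.16: 1.96 × √(0.00296 + 0.00258) = 0.146, or 14.6 points
- 0.38 v 0.28: 1.96 × √(0.00453 + 0.00388) = 0.180, or 18.0 points

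An artefact of 3 to 10 points is thus smaller than the sampling uncertainty and would seldom produce a significant result by itself. It would still shift the estimate, and the interval makes no allowance for it.

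**The case against.** The strongest reply is that the plan already has common ascertainment and a standardized pathway, and that these are secondary listings with no power claim and no specific aim naming them. Much of this stands, and it limits what can be said.

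- **A reader might infer that opioid effects have no common schedule at all.** That is too broad: OBAS asks both arms about them at 24 hours. But it is a single postoperative self-report by unblinded patients, it enters the analysis as a composite, and a patient questionnaire is a weak source for respiratory depression and for sedation as staff observe it.
- **A reader might infer that antiemetic prophylaxis is chosen knowing the arm.** The core regimen is not. Only scopolamine, which is directed at high-risk patients, and the background propofol infusion are discretionary prophylaxis; the PACU drugs are rescue treatment. Any effect of these would bear on nausea and vomiting. Giving more of them with ITA could also fairly be seen as part of the strategy being compared, not as bias.
- **A reader might infer that ITA patients will be watched more closely.** No section sets arm-specific monitoring. The oxycodone timing makes it plausible and no more.
- **A reader might combine these into two opposing biases and conclude that no harm result could be trusted.** The documents do not support this. Masking by antiemetics can be argued only for nausea and vomiting, and neither mechanism has a known size.

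What survives is the narrower gap: undefined, unscheduled events, known allocation, arm-dependent early care and a planned between-arm test.

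**Conclusion.** The concern holds in this limited form, and most clearly for sedation and respiratory depression. It is a weakness in how secondary safety outcomes are collected. It does not touch the sample size or the primary non-inferiority test. It is worth correcting before enrolment, because data not collected on a common schedule cannot be recovered afterwards.

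The size and direction of any distortion are unknown. The 3 to 10 points above rest wholly on assumed true rates of 20% to 40%, equal in both arms, and assumed detection of 95% against 70% to 80%. Milder assumptions give 1 point, and equal detection gives none.

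**What to change.** In C.2, Outcomes:
- Record nausea/vomiting, itching, a sedation score and respiratory rate at the existing 4, 8, 16 and 24 hour assessments in both arms.
- Give one written definition for each event, and name the sedation scale and the assessor.
- Make these scheduled values the main between-arm comparison. Report events charted between assessments as supplementary: they may include important events that fall between the set times, but they remain open to unequal charting.

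In the Statistical analysis plan, add a table by arm of actual use of scopolamine, background propofol and rescue antiemetics, so that nausea results can be read beside it. This is reporting only. It changes neither who receives these drugs nor when that is decided.

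The cost is a few items at four assessments that already take place, so each becomes slightly longer, plus extraction of antiemetic use from the record. A common schedule equalizes the occasions for observation. It does not remove the influence of known allocation on subjective ratings, and the report should say so.

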**Statistical analysis plan**

Data will be summarized using standard descriptive statistics by reporting mean (SD) or median (IQR) for continuous variables and frequency and percentages for categorical variables. Continuous variables will be compared between the two treatment arms using the two-sample t-test or the Wilcoxon rank sum test as appropriate. Categorical variables will be compared between the two treatment arms using the chi-square test or the Fisher's exact test. For the primary outcome, the mean OBAS score between the two groups will be presented along with the upper limit of the 95% confidence bound for the mean difference. We will conclude non-inferiority if this upper limit is less than the predefined limit for non-inferiority. Multivariable regression models will be fit to assess for differences in outcomes if there are unbalanced baseline covariates in the two treatment arms.

The primary analysis will be restricted to per-protocol patients and will mirror that of the POP-UP trial, which was a non-inferiority trial that evaluated the effectiveness of continuous wound infiltration in patients undergoing hepato-pancreato-biliary surgery. An intention-to-treat analysis will be performed as a secondary analysis based on the rationale that such an analysis in a non-inferiority trial might introduce bias to no difference.

A thorough review of the data for inconsistencies and outliers will be performed by the statistical team prior to the formal analysis. Data issues will be resolved by the primary investigator and study coordinator. The extent of missing data will be examined and sensitivity analyses of the primary and secondary outcomes will be conducted using multiple imputation if warranted. All statistical analyses will be performed using SAS or R.

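### Aim 3 concerns cost, but no cost-specific method or between-arm cost estimate is prespecified, and the generic rule could end in medians and a rank p-value

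*Combined protocol and SAP*

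**What the plan says.** - **Aim.** Specific Aims, item 3: "Report the impact of ITA use on cost". The aim names no summary measure (mean, median or ratio).
- **Status.** The Background lists "length of stay, cost, and patient satisfaction as secondary outcomes". It also gives expense as one of the drawbacks of ITA.
- **Endpoints.** Under Outcomes, the cost analysis comprises "OR time and surgical time" and "Total and pain management related standardized costs".
- **Generic rule.** The Statistical analysis plan summarises data by "reporting mean (SD) or median (IQR) for continuous variables" and adds: "Continuous variables will be compared between the two treatment arms using the two-sample t-test or the Wilcoxon rank sum test as appropriate". It gives no criterion for choosing and no exception for costs.
- **Effect estimate.** This is promised for one endpoint: "For the primary outcome, the mean OBAS score between the two groups will be presented along with the upper limit of the 95% confidence bound".
- **Modelling.** "Multivariable regression models will be fit to assess for differences in outcomes if there are unbalanced baseline covariates in the two treatment arms". This is conditional on imbalance, and no model family, link or cost scale is given.

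**The concern.** A statement about cost impact needs an estimate in cost units. The arithmetic mean difference per patient is the natural one, because multiplied by the number of patients it gives total spend. Two medians and a Wilcoxon p-value do not provide it.

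The two approaches could plausibly diverge here. ITA adds an injection in the operating room for nearly every patient in its arm. It might also change infrequent, costly events that the Outcomes section tracks, such as ileus, spinal headache or a longer stay. A small shift for everyone combined with a change in the tail is the setting in which ranks and means can disagree. At stake is whether the trial's statement on cost, which is part of its rationale, describes spending or only the typical patient's rank. The choice of test is also left until the data are seen, in an unblinded trial.

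**Working it through.** **Plan's own figure.** None is given for cost. The arm size used below was checked first. Inputs from Sample size calculation: margin 3, SD 5, one-sided alpha 0.05, power 90%.
- Normal approximation: n = 2 × SD² × (z₀.₉₅ + z₀.₉₀)² / margin² = 2 × 25 × (1.645 + 1.282)² / 9 = 47.6, so 48 per group.
- Exact t: 49 per group (power 0.904), as stated. Then 49 × 1.05 = 51.45, so 52 per arm, as stated.

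**Assumptions for the illustration.** Costs are lognormal with log-SD sigma. There are 52 per arm, 4,000 simulated trials per scenario, and two-sided 0.05 tests. The cost shape is not in the documents, so a range is shown. For a lognormal, mean = median × exp(sigma²/2).

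**A. Equal mean cost, so any signal about mean cost is false**

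| sigma, arm 1 vs arm 2 | Wilcoxon p<0.05 | Comparison of means (Welch) p<0.05 |
|---|---|---|
| 0.5 vs 0.5 | about 5% | about 5% |
| 0.4 vs 0.5 | 7% to 8% | 5% to 6% |
| 0.4 vs 0.7 | about 30% | about 6% |
| 0.3 vs 0.7 | about 45% | about 6% |

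**B. Equal medians, unequal means.** Sigma 0.5 vs 1.0: the means are exp(0.125) = 1.133 and exp(0.5) = 1.649 times the common median. The ratio is 1.649 / 1.133 = 1.455, so mean cost is about 45% higher in one arm. Wilcoxon rejects in about 6% of trials, close to its error rate. Welch rejects in 37% to 38%.

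**C. Proportional shift of 1.2 with the same sigma in both arms.** The tests agree in direction and have similar power: at sigma 0.5, Wilcoxon 43% and Welch 40%. The median difference is 0.20. The mean difference is 0.2 × exp(sigma²/2), which is 0.23 at sigma 0.5 and 0.33 at sigma 1.0. The median therefore understates the change in spend even when the tests agree.

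**D. Fixed extra cost with a smaller tail.** ITA adds 1.5 units to every patient and halves a 15% risk of a 20-unit prolonged stay. The mean difference is 1.5 − 0.075 × 20 = 0. With a normal baseline cost of SD 2, 3, 4 or 5, Wilcoxon rejects in about 59%, 25%, 13% or 8% of trials, and a comparison of means in about 5%. The result depends almost wholly on the assumed baseline SD, so no single figure from this scenario should be quoted alone.

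**Precision of a mean comparison.** Across scenarios A to C, including sigma 0.5 vs 0.8 and 0.5 vs 1.0 with equal means, the Welch 95% interval covered the true mean difference in 91% to 96% of trials. It was lowest (91.4%) in scenario B, which is a reason to prefer a bootstrap interval. Bootstrap coverage itself was not simulated.

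**The case against.** A reader might infer that the plan sends costs to a rank test, or that it specifies a wrong method. It does not. The test is to be chosen as fits the data, no skewness criterion is set, and mean (SD) with a t-test remains open. A reader might also infer that Aim 3 asks for mean cost. It does not name the mean, and its verb is descriptive. Preferring the mean is a methodological judgement, though a well-founded one.

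Skewness, and above all unequal spread, are assumed. Some planned high-cost cases are excluded (planned ICU admission, exenteration, HIPEC), and costs are standardized, so the tails may be modest. With similar spreads the false-signal problem almost disappears (A, first two rows), and under a common proportional shift the tests agree (C). The prolonged-stay argument also applies less clearly to pain-management cost than to total cost.

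All of this stands and limits the size of the point. It does not supply what is missing: whichever test is chosen, no between-arm cost difference with an interval is promised.

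**Conclusion.** The point holds as a gap in specification. Aim 3 has no cost-specific method, and an effect estimate with a confidence bound is planned only for OBAS. If costs are skewed, ordinary use of the generic rule would give medians and a rank p-value, with no difference in cost units.

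How misleading that would be depends on assumed shapes. With equal means, the excess of Wilcoxon signals runs from nil (equal spreads) to about 40 percentage points (45% against about 6%, sigma 0.3 vs 0.7). In the other direction, a mean about 45% higher in one arm can go almost undetected (about 6%). The documents do not show which case applies, so these figures illustrate what can happen and do not predict it. The matter is confined to a secondary aim. The OBAS analysis and the 104 participants are unaffected. Label: cheap improvement.

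**What to change.** Add to the Statistical analysis plan: the two standardized cost endpoints (total, and pain management) will each be reported as the difference in arithmetic mean cost per patient, ITA+ILB minus ILB, with a bootstrap 95% confidence interval, resampling within arm. Medians (IQR) are descriptive, and any rank test is supportive only. A gamma log-link model adjusted for the two stratification factors is an optional extra.

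This costs one sentence and a short routine, with no new data and no change to the sample size. The drawback is that the interval may be wide if a few patients have very high costs. That width is the precision the trial actually has on mean cost.
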